3.3. Interim Analysis of Data

No prespecified interim analysis of unblinded data during the DB treatment phase is planned by the clinical team. However, depending on the recruitment, or in support of regulatory filings for upcoming studies, or for any other reason the Sponsor deems necessary, an unblinded review of safety and biomarker data prior to the last subject's completion of the DB treatment phase might be conducted by an internal Interim Analysis Committee. If any such review is conducted it will be documented in an Interim Analysis Committee charter prior to the unblinding. The constitution of the Interim analysis committee will be documented in the Interim Analysis Committee charter and may include Sponsor study team members.

As noted in Section 5, when the parent study (eg, 54861911ALZ2002 and potential future Phase 1b and 2 studies) is completed and its clinical database is closed, the randomization codes from the parent study will be released to the sponsor study team. Thus, the sponsor will be unblinded at that time, but the investigator and subjects will continue to be blinded to treatment during the DB treatment phase, until the last subject has completed that phase, and the database from that phase has been reviewed, corrected as necessary, and locked. At that point, the sponsor will perform analyses of key safety, biomarker, and efficacy variables, as detailed in a prespecified statistical analysis plan.

Following the sponsor's review of these analyses, information on an individual subject's treatment allocation during the DB phase will be made available upon request by the investigator. As subjects that remain in the study will all be receiving open label JNJ-54861911

at that time, and as no change or alteration of the locked database from the DB phase will be possible, there should be no bias introduced by this measure.

3.4. Stopping Criteria

3.4.1. Individual Criteria for Stopping Study Treatment

In this Phase 2 study the following specific individual rules for stopping study treatment will apply (see Section 10.2 for details):

- A subject has a mean QTcF interval of >500 msec if confirmed upon repeat ECG, and/or mean QTcF increase versus baseline of >60 msec if confirmed upon repeat ECG, after consultation with the sponsor's medical monitor (all based on triplicate recordings).
- The investigator believes that for safety reasons (e.g., adverse event) it is in the best interest of the subject.
- Between Weeks 52 and 64, treatment must be discontinued if any of the following occurs:
 - ALT or AST $>5\times$ ULN
 - ALT or AST $>3\times$ ULN and total bilirubin $>2\times$ ULN or international normalized ratio (INR) >1.5
 - ALT or AST $>3\times$ ULN with the appearance of fatigue, nausea, vomiting, right upper quadrant pain or tenderness, fever, rash, and/or eosinophilia $>5\%$
- After Week 64, treatment must be discontinued if any of the following occurs:
 - ALT or AST $>8\times$ ULN
 - ALT or AST $>5\times$ ULN for more than 2 weeks
 - ALT or AST $>3\times$ ULN and total bilirubin $>2\times$ ULN or INR >1.5
 - ALT or AST $>3\times$ ULN with the appearance of fatigue, nausea, vomiting, right upper quadrant pain or tenderness, fever, rash, and/or eosinophilia $>5\%$
- A subject who meets any of the withdrawal criteria described in Section 10.3.

Events of elevated liver enzymes or increased QTc that require subjects to discontinue will be considered as serious and will be reported to Sponsor within 24 hours of the knowledge of the event.

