Eligible subjects enrolled in this study will receive either JNJ-54861911 (10 mg or 25 mg q.d.) or placebo (q.d.). Subjects will continue with their current treatment regimen established in the parent JNJ-54861911 study (e.g. for 54861911ALZ2002 placebo or JNJ-54861911) for a period of 52 Weeks (12 Months) (placebo-controlled DB treatment phase). Subjects who have received an active dose different from 10-mg or 25-mg JNJ-54861911 in 54861911ALZ2002 study will be receiving the closest dose available in DB treatment phase (10-mg or 25-mg JNJ-54861911; e.g., subjects receiving 50 mg in study 54861911ALZ2002 will be assigned to 25 mg JNJ-54861911).

Following the initial 52-Week (12-Month) treatment phase (DB treatment phase) in this study, subjects receiving placebo in the DB treatment phase will be randomized with equal chance to one of 2 active JNJ-54861911 dose levels (i.e., 5-mg q.d JNJ-54861911 or 25-mg q.d. JNJ-54861911) for continuous treatment in OL phase. As such during OL phase, all subjects will receive active (JNJ-54861911) treatment (open-label). In addition, subjects who were receiving 10 mg q.d. JNJ-54861911 will have their dose reduced to 5 mg q.d. in order to harmonize the dosage with that of the Phase 2b/3 program, while subjects who were receiving 25 mg q.d. will continue to receive that dosage.

During the Treatment Phases (DB and OL treatment phases), primarily safety and tolerability will be monitored at regular intervals (e.g., MRI, physical and neurological examination, suicidality risk assessment, vital signs, 12-lead ECG, safety labs, dermatologic and ophthalmologic examinations). Pharmacokinetics (CSF and plasma), and PD effects by means of biomarkers (fluid [CSF and plasma samples] and imaging (volumetric MRI)) will be explored at the time points listed in the Time and Events Schedule. In addition, effects of JNJ-54861911 on cognition (e.g., Repeatable Battery for the Assessment of Neuropsychological Status (RBANS), Mini Mental State Examination (MMSE) and California Verbal Learning Test – Second Edition [CVLT-II]) will be assessed at regular intervals. The subject's clinical status will be assessed during the study by means of the Clinical Dementia Rating Scale (CDR). Investigators will

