Specific dermatologic and ophthalmologic examinations, as described in Section 9.2, Safety Evaluations have been implemented in this study as potential BACE1- or BACE2-linked toxicities (e.g. melanin deposition changes and retinal abnormalities) have been described in the literature (e.g. BACE1 or BACE2 knock-out mice). With the exception of fur discoloration resulting in progressive lightening of the fur from normal dark brown to paler cream or grey, which was seen in one species only (Tg mice in the 6 month carcinogenicity study), however, these toxicities have not been observed in nonclinical chronic studies with JNJ-54861911. Note that cases of lightening of skin, lightening of hair or ophthalmological adverse events are considered adverse events of special interest (AESI) and are subject to reporting timelines as described in Section 12.3.4.

As a result of the newly identified case of drug-induced hepatotoxicity, if at any time during treatment a subject has an ALT or AST result that is $\geq 3 \times$ ULN, the test should be repeated within 24 - 72 hours and, if confirmed, the further evaluation and management procedures described in [Attachment 1](#) should be followed.

In addition to the (safety) MRI assessments performed under the 54861911ALZ2002 study (if applicable), safety MRIs will be collected in this study during both DB and OL treatment periods, as indicated in the Time and Events Schedule, to monitor any treatment-emergent abnormalities including ARIA-edema or effusion (E) and ARIA-hemosiderin (H). Additional annual MRIs will be collected in OL period. If any safety related changes are observed (e.g. ARIA-E), additional safety MRIs may be collected at a frequency recommended by the DRC.

In case of any changes observed in any of the safety measures performed that are considered not clinically significant or do not have a direct clinical symptomatology as assessed by the investigator, they should be closely monitored, with a potential increased safety monitoring frequency as deemed appropriate by the investigator. In addition, these findings will be presented to the DRC, who will make recommendations regarding the safety and continuation of the study as per its charter.

Biomarker Collection

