10.2. Discontinuation of Study Treatment

If a subject's study treatment must be discontinued before the end of the treatment regimen, this will not result in automatic withdrawal of the subject from the study.

The following specific individual rules for stopping study treatment will apply:

- Mean QTcF interval of > 500 msec if confirmed upon repeat ECG, and/or mean QTcF increase versus baseline of > 60 msec if confirmed upon repeat ECG (all triplicate recordings).
- The investigator believes that for safety reasons (e.g., adverse event) it is in the best interest of the subject.
- Liver enzyme elevation between Weeks 52 and 64, including any of the following:
 - ALT or AST $>5\times$ ULN
 - ALT or AST $>3\times$ ULN and total bilirubin $>2\times$ ULN or INR >1.5
 - ALT or AST $>3\times$ ULN with the appearance of fatigue, nausea, vomiting, right upper quadrant pain or tenderness, fever, rash, and/or eosinophilia $>5\%$
- Liver enzyme elevation after Week 64, including any of the following:
 - ALT or AST $>8\times$ ULN
 - ALT or AST $>5\times$ ULN for more than 2 weeks
 - ALT or AST $>3\times$ ULN and total bilirubin $>2\times$ ULN or INR >1.5
 - ALT or AST $>3\times$ ULN with the appearance of fatigue, nausea, vomiting, right upper quadrant pain or tenderness, fever, rash, and/or eosinophilia $>5\%$

Re-initiation of study treatment should only be done after consultation with the sponsor medical monitor and in mutual agreement between the sponsor and the study center. If a subject permanently discontinues study treatment before the end of the treatment phase, the subject will be asked to complete the Week 52 assessments, including CSF sampling, if not yet obtained earlier. At a minimum, the subject will be asked to complete the End-of-Treatment Visit (Follow-up visit) as per the Time and Events Schedule.

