	$\geq 5 \times \text{ULN}$	$\geq 3, < 5 \times \text{ULN}$	$> 1, < 3 \times \text{ULN}$	WNL
Blood sampling frequency	2× per week	1× per week	Once every 2 weeks until sponsor approves reduction to 1× per month	1× per month until 3 consecutive months within normal limits, then Resume the standard, per protocol schedule
Frequency of site contact with medical monitor	1× per week	1 x per week	1× per month	Once, just prior to resumption of the standard, per protocol schedule
Abbreviations: ALT=alanine aminotransferase, AST=aspartate aminotransferase; ULN=upper limit of normal; WNL=within normal limits				

3. Hepatology/Gastroenterology Consult

Mandatory, urgent hepatology/gastroenterology consult must be conducted if any of the following occurs:

- AST or ALT $\geq 8 \times \text{ULN}$
- AST or ALT $\geq 3 \times \text{ULN}$ with symptoms
- AST or ALT $\geq 3 \times \text{ULN}$ and total bilirubin $\geq 2 \text{ mg/dL}$
- AST or ALT $\geq 5 \times \text{ULN}$ persists for > 1 week
- AST or ALT $\geq 3 \times \text{ULN}$ persists for > 2 weeks

4. Discontinuation of Study Treatment:

Between Weeks 52 and 64, treatment must be discontinued if any of the following occurs:

- ALT or AST $> 5 \times \text{ULN}$
- ALT or AST $> 3 \times \text{ULN}$ and total bilirubin $> 2 \times \text{ULN}$ or INR > 1.5
- ALT or AST $> 3 \times \text{ULN}$ with the appearance of fatigue, nausea, vomiting, right upper quadrant pain or tenderness, fever, rash, and/or eosinophilia $> 5\%$

After Week 64, treatment must be discontinued if any of the following occurs:

- ALT or AST $> 8 \times \text{ULN}$

- ALT or AST $> 5 \times$ ULN for more than 2 weeks
- ALT or AST $> 3 \times$ ULN and total bilirubin $> 2 \times$ ULN or INR > 1.5
- ALT or AST $> 3 \times$ ULN with the appearance of fatigue, nausea, vomiting, right upper quadrant pain or tenderness, fever, rash, and/or eosinophilia $> 5\%$

5. SAE Reporting

Subjects who meet the criteria for discontinuation of study treatment should have the event reported as an SAE and should follow the SAE reporting process as outlined in Section 12.3.2 of the protocol.

6. Continuation or Resumption of Study Treatment:

Study treatment may continue in asymptomatic subjects who do not meet the discontinuation rules, however, the investigator/site must adhere to the blood sampling and contact with Medical Monitor schedule in [Table 1](#).

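### The mandatory liver-enzyme stopping rules begin only at Week 52, so none applies during the double-blind year

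*Protocol*

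**What the plan says.** Three places in the protocol set mandatory liver-enzyme discontinuation rules, and they agree with one another.

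- Section 3.4.1: "Between Weeks 52 and 64, treatment must be discontinued if any of the following occurs", followed by a separate list for the period after Week 64.
- Section 10.2: "Liver enzyme elevation between Weeks 52 and 64, including any of the following" and "Liver enzyme elevation after Week 64, including any of the following".
- Attachment 1 item 4: the same Weeks 52 to 64 list, then "After Week 64, treatment must be discontinued if any of the following occurs".

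The Weeks 52 to 64 set has three criteria: ALT or AST above 5× ULN; above 3× ULN with total bilirubin above 2× ULN or INR above 1.5; above 3× ULN with listed symptoms or eosinophilia above 5%. The after-Week-64 set replaces the first of these with two: above 8× ULN, and above 5× ULN for more than 2 weeks.

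The work-up has no such time limit. Section 3.2 triggers it "if at any time during treatment a subject has an ALT or AST result that is" at or above 3× ULN and, once that is confirmed, sends the subject to Attachment 1. Item 6 there says: "Study treatment may continue in asymptomatic subjects who do not meet the discontinuation rules".

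**The concern.** The double-blind phase runs from Day 1 to Week 52, and Section 3.1 has subjects on 10 mg or 25 mg of active drug throughout it. The protocol treats the liver as this drug's known problem. Section 12.3.5 classes elevated liver enzymes as an identified adverse drug reaction. Section 1.1 reports 11 subjects above 3× ULN in studies longer than one month (9 on active drug, 1 on placebo, 1 still blinded) and a biopsy-based case of drug-induced hepatotoxicity on 25 mg.

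If the stopping rules start only at Week 52, a blinded investigator who follows the text has no threshold at which dosing must end during a full year of exposure. Item 6 then reads as permission to continue an asymptomatic subject, because before Week 52 there is no liver rule to meet. The QTcF stop, in the same list in Section 3.4.1, carries no time window; only the liver stop does.

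The 10 mg dose is affected most. Under Sections 3.1 and 5 it is cut to 5 mg on entry to the open-label phase, so 10 mg is given only in the period without a mandatory liver rule.

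**Working it through.** No figure in the protocol needs reproducing; the check is one of coverage.

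**Step 1. Count the mandatory liver criteria by window.** The counts are the same in Section 3.4.1, Section 10.2 and Attachment 1 item 4.

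| Window | Treatment | Mandatory liver criteria |
|---|---|---|
| Day 1 to Week 52 | 10 mg, 25 mg or placebo, blinded | 0 |
| Weeks 52 to 64 | 5 mg or 25 mg, open label | 3 |
| After Week 64 | 5 mg or 25 mg, open label | 4 |

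**Step 2. Place the scheduled chemistry draws.** After Day 1, the Time and Events Schedule and Section 9.1.3 give Weeks 8, 16, 24, 36 and 52. Four of the five (Weeks 8, 16, 24, 36) fall before the first window opens. The Week 52 draw sits on its boundary.

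**Step 3. Run two hypothetical asymptomatic subjects through items 4 and 6 of Attachment 1.**

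| Profile | Week 24 | Week 60 | Week 70 |
|---|---|---|---|
| A: ALT 9× ULN | no rule met, may continue | must stop (9 > 5) | must stop (9 > 8) |
| B: ALT 4× ULN, bilirubin 2.5× ULN | no rule met, may continue | must stop (4 > 3 and 2.5 > 2) | must stop (4 > 3 and 2.5 > 2) |

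**Step 4. Ask what else would happen to them at Week 24.** Attachment 1 outside item 4 has no week limit, so both get the repeat test and full work-up. Item 3 adds: "Mandatory, urgent hepatology/gastroenterology consult must be conducted if any of the following occurs".

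- Profile A meets the 8× ULN consult trigger at once. Under Table 1 it has twice-weekly sampling and weekly medical-monitor contact.
- Profile B has weekly sampling and weekly contact. Its consult is triggered if bilirubin reaches 2 mg/dL. At 2.5× ULN that requires a laboratory ULN of at least 2 / 2.5 = 0.8 mg/dL; the protocol does not give the ULN. Otherwise the consult follows if ALT stays at or above 3× ULN for more than 2 weeks.
- For both, the investigator may stop treatment on safety grounds (Sections 3.4.1 and 10.2).

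None of these provisions requires dosing to stop.

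**Step 5. Look at what depends on the criteria.** Section 12.3.2 and Attachment 1 item 5 make an event serious when the discontinuation criteria are met. Before Week 52 that route cannot be triggered by a liver result. Section 12.3.5 still catches a liver-related discontinuation, but only once someone has decided to stop.

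**The case against.** The strongest reply is that the windows have a reason. In the hepatotoxicity case described in Section 1.1 the enzymes rose in Month 1, and the response was aimed at the first 3 months of dosing. Weeks 52 to 64 are when former placebo subjects first receive active drug, whereas active-arm subjects from the parent study (54861911ALZ2002) had already completed 6 months. This explains why the stricter set belongs at Weeks 52 to 64. It does not explain having no set at all before then: the after-Week-64 criteria apply indefinitely to subjects with longer exposure, and a subject on continuous 25 mg has no threshold at Week 51 but has one at Week 53.

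Second, other safeguards are substantial. Besides those in Attachment 1, there is Data Review Committee oversight and the hepatic exclusion criterion. Item 6 also permits continuation only in asymptomatic subjects, so a symptomatic subject above 3× ULN is not expressly allowed to carry on. That stands, and it makes the gap clearest for asymptomatic subjects.

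Third, few subjects may be affected. Section 1.1 lists the parent study as completed by 6 September 2017 and no other Phase 1b or stand-alone Phase 2 study as ongoing, while Section 4.1 requires entry within 6 weeks of completing one (12 with approval). This also stands as a limit on size. However, the protocol gives no completion date for the parent study, still admits subjects from future studies, and in Section 3.3 treats the end of the double-blind phase as yet to come.

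**Conclusion.** The concern holds. The current text contains no mandatory liver-enzyme stop from Day 1 to Week 52, while the same results after Week 52 require one. The size is 0 criteria against 3 and then 4, and it is clearest in asymptomatic subjects with marked elevations or with raised bilirubin. The conclusion rests on reading the windows literally and on the double-blind phase being open to current or future subjects. The number exposed under this text is not stated and cannot be derived, and no event rate by arm is available.

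This is a participant-safety matter. Because every blinded arm follows the same rules, it does not bias the active-placebo comparison. It should be fixed; the remaining safeguards keep it from being more serious than that.

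**What to change.** In Section 3.4.1, Section 10.2 and Attachment 1 item 4, apply at least the existing after-Week-64 criteria from Day 1 to Week 52: ALT or AST above 8× ULN; above 5× ULN for more than 2 weeks; above 3× ULN with total bilirubin above 2× ULN or INR above 1.5; above 3× ULN with the listed symptoms or eosinophilia above 5%. The sponsor's safety team may prefer the stricter Weeks 52 to 64 set, particularly for subjects from future parent studies with shorter prior exposure. State which set governs the Week 52 draw. Item 6 of Attachment 1 and the reference to Section 10.2 in Section 12.3.2 then work in every phase without further change.

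The cost is a protocol amendment with wording in three places, a letter to sites, and possibly a few more mandatory discontinuations in the double-blind phase. No new tests are needed. ALT, AST, total bilirubin and the white-cell differential are in the routine panels (Section 9.2.9), INR is in the Attachment 1 repeat sample, and the twice-weekly sampling in Table 1 at or above 5× ULN already supports the 2-week criterion.

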3.4.2. Protocol Stopping Criteria

A DRC will be established to monitor data on an ongoing basis to ensure the continuing safety of the subjects enrolled in this study (see Section 11.7, Data Review Committee). The committee will meet periodically to review interim data. After the review, the DRC will make recommendations regarding the safety and continuation of the study. The details will be provided in a separate DRC charter.

4. SUBJECT POPULATION

Subjects in the early AD spectrum, i.e., subjects asymptomatic at risk for Alzheimer's dementia and prodromal AD subjects at time of enrollment under the parent protocol, who have completed a Phase 1b or Phase 2 clinical study with JNJ-54861911 will be provided the opportunity to participate in this study. Subjects that have progressed to dementia in the parent protocol (CDR \geq 1) or who are incapable of providing informed consent will not be enrolled.

The inclusion and exclusion criteria for enrolling subjects in this study are described in the following 2 subsections. If there is a question about the inclusion or exclusion criteria below, the investigator should consult with the appropriate sponsor representative before enrolling a subject in the study. In case the subject progresses to a dementia state during the study, the subject may remain in the study, provided that the investigator judges that the potential benefits of treatment for this subject clearly outweigh the known and foreseeable risks and assent or consent (as applicable) for continued participation is obtained from a representative determined in accordance with the local law. In cases where a subject has progressed to dementia, treatments indicated for this condition (e.g., memantine or cholinesterase inhibitors) are permitted after notification of the sponsor.

For a discussion of the statistical considerations of subject selection, refer to Section 11.2, Sample Size Determination.

4.1. Inclusion Criteria

Each potential subject must satisfy all of the following criteria to be enrolled in the study.

1. Criterion modified per amendment.
 - 1.1 Subjects in the early AD spectrum at time of enrollment meeting all pertinent inclusion and exclusion criteria of the parent protocol, must have very recently completed their treatment in a Phase 1b or Phase 2 JNJ-54861911 clinical study (e.g., 54861911ALZ2002) under the parent protocol. Enrollment in this study should be completed (Day 1 of DB treatment phase) as soon as possible, but within 6 weeks, following completion of their treatment period under the parent protocol. If not defined under the parent protocol, completion of the treatment period is defined as having completed all study related procedures of the last visit of the treatment period under the parent protocol. A screening phase of up to 12 weeks may be allowed following written approval of the Sponsor.
2. Subject must be willing and able to adhere to the prohibitions and restrictions specified in this protocol.
3. Criterion modified per amendment.

- 3.1 Each subject must sign an informed consent form (ICF) indicating that he or she understands the purpose of and procedures required for the study and are willing to participate in the study.
4. Subjects must have a reliable informant (relative, partner, or friend). The informant must be willing to participate as a source of information and has at least weekly contact with the subject (contact can be in-person, via telephone or other audio/visual communication). The informant must have sufficient contact such that the investigator feels he/she can provide meaningful information about the subject's daily function. If possible, an alternate informant meeting these criteria who can replace the primary informant should be identified prior to randomization.

